Investigators and Trial Centres: The overall design and conduct of this investigator-initiated study will be the responsibility of the Steering Committee. This a collaborative trial designed and coordinated jointly by independent investigators at the National Institute of Health Innovation (University of Auckland), the Dept. of General Practice and Primary Care (University of Auckland), and Auckland District Health Board, with input from clinicians at Auckland DHB, Counties Manukau DHB, Waikato DHB, the Nurse Maude Association Christchurch, and the Southern DHB. Publication of data from this trial will be the responsibility of the Steering Committee. The trial will be co-ordinated from the NIHI, with participants recruited from patients attending the district nursing services at Auckland DHB, Counties Manukau DHB, Waikato DHB, the Nurse Maude Association Christchurch, and the Southern DHB.

Trial Period: Oct 2014 – Oct 2017

Clinical Phase: Phase III

Objectives: The objective of this trial is to determine the effectiveness of low dose aspirin compared to placebo when used in addition to compression therapy for venous leg ulcer healing.

Duration of Treatment: The maximum duration of treatment is 24 weeks (or less if the ulcer heals within 24 weeks).

Trial Design and Methodology

A prospective community-based, double-blind, placebo-controlled, randomised trial with participants receiving either 150 mg aspirin daily for up to 24 weeks or matching placebo. Block randomisation will be used, stratified by trial centre and prognostic index (ulcer size and duration) to ensure a balance of participants within trial centres and for participants likely to be slow healers. Participants in both arms will also receive compression therapy (with system of choice guided by patient and/or clinical preference) as delivered through district nursing services at the trial centres. Assessment of health-related quality of life will be carried out at baseline and at the end of the trial treatment period. The patient will continue to receive district nursing care as per normal protocol.

Inclusion/exclusion criteria: Patients with leg ulcers will be eligible for *inclusion* if they meet the following criteria:

- Aged 18 years or older
- Determined to have a venous leg ulcer (clinical indications of venous ulceration, ABI \geq 0.8, and other causative aetiologies ruled out)
- Able to tolerate compression therapy
- Able to provide written informed consent

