- Confirmation with participant's general practitioner that the participant can take low dose aspirin or placebo.

Potentially eligible participants will be *excluded* if they meet any of the criteria below:

- Pregnant or breast-feeding women
- History of myocardial infarction, stroke, transient ischaemic attack, angina or significant peripheral arterial disease
- History of adverse effects related to aspirin use

- Currently using aspirin, or other anti-platelet or anticoagulant therapy
- Participant has any other existing condition or treatment that is a contraindication to use of aspirin or to participation in the trial
- Participant has any other existing condition where treatment with aspirin is indicated.

Test Product:

- Aspirin 150 mg daily + compression bandaging

Reference Therapy:

- Placebo daily + compression bandaging

Primary Outcome:

Time to complete healing over 24 weeks. Complete healing is defined as full epithelialisation of the ulcer with no scab.

Secondary outcomes:

- Proportion with healed reference VLU at 24 weeks
- Change in estimated reference ulcer area from baseline to 24 weeks
- Adherence with aspirin
- Change in health-related quality of life from baseline to 24 weeks
- Adverse events
- Efficacy of blinding.

Sample size: A sample size of 354 (177 in each group) will be sufficient to show a **four week** difference in time-to-healing at 90% power with an alpha of 0.05, assuming the median time-to-healing in the control group over a six month follow up is 92 days and allowing for 10% loss to follow up.

Statistical analysis: All analyses will use intention-to-treat in accord with a Statistical Analysis Plan developed *a priori*. Time-to-event data will be analysed using Kaplan Meier plots, log rank test and Cox regression. Simple incidence rates, relative risks and 95% CIs will be obtained for all binary variables in the first instance, with multiple logistic regression analysis if necessary to adjust for imbalance. Continuous outcomes will be analysed using multiple linear regression and adjusted for baseline value and other covariates if needed. A *kappa* will be calculated for the evaluation of the efficacy of blinding.

2. Background

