6.3 Eligibility criteria

Patients with leg ulcers will be eligible for *inclusion* if they meet the following criteria:

- Aged 18 years or older
- Determined to have a venous leg ulcer (clinical indications of venous ulceration, ABI \geq 0.8, and other causative aetiologies ruled out)
- Able to tolerate compression therapy
- Able to provide written informed consent
- Confirmation with participant's general practitioner that the participant can take low dose aspirin or placebo.

Potentially eligible participants will be *excluded* if they meet any of the criteria below:

- Pregnant or breast-feeding women
- History of myocardial infarction, stroke, transient ischaemic attack, angina or significant peripheral arterial disease
- History of adverse effects related to aspirin use
- Currently using aspirin, or other anti-platelet or anticoagulant therapy
- Participant has any other existing condition or treatment that is a contraindication to use of aspirin or to participation in the trial
- Participant has any other existing condition where treatment with aspirin is indicated.

7. Randomisation and allocation concealment

On registration (week -1) participants will be assigned a unique sequential registration number using numbers generated by the NIHI data management. When a registration number has been allocated, the participant's initials and date of birth and the date of registration must be recorded. This registration number will be used to identify the participant throughout all periods of the trial. Once a registration number has been assigned, it may not be used again.

Immediately after baseline data have been recorded, consented patients who fulfil entry criteria will be randomised by computer to one of the two trial groups using stratified blocked randomisation with varying block sizes of 2 and 4. The randomisation sequence will be prepared by the trial statistician and loaded into a secure database. Randomisation will be stratified by trial centre and prognostic index (based on ulcer and duration) which will isolate any centre effect in clinical management and ensure a balance on key prognostic variables known to influence healing at 24 weeks. Each treatment pack is uniquely numbered and is allocated using the randomisation sequence. The Research Nurse accesses the randomisation web-page, completes data entry, and generates the allocation using a computerised tablet. The allocated treatment is then given to the participant by the Research Nurse.

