10.1 Baseline assessments

Screening information will be obtained from a telephone contact with the patient at week -1. Eligible patients will be visited at Week -1 and, once consented, the following baseline data will be collected immediately prior to randomisation:

- Demography: age, sex, self-reported ethnicity.
- Ulcer area and duration: Reference VLU area (area > 5 cm²) and duration (duration for > six months) provide data for a prognostic index for VLU healing with 24 weeks of compression.⁵⁸ The index assigns scores of 0, 1 or 2 based on absence of both factors, presence of one factor, or presence of both factors. Sophisticated tools for measuring ulcer area are either too expensive (e.g. SilhouetteTM) or no longer supported by the manufacturer in New Zealand (e.g. VisitrakTM). A simpler method of estimation using the formula for area of an ellipse has been shown to be highly correlated with ulcer area, both in the literature ($r = 0.951$)⁵⁰ and internal data from one of our previous trials ($r = 0.92$).⁸ Ulcer duration will be obtained from patient recall. Where more than one VLU is present, the largest ulcer will be the reference ulcer.
- ABI: An ABI < 0.8 indicates that there is a high probability that some arterial insufficiency is present (positive predictive value = 95% in a general practice population).⁵⁹ Use of compression therapy where significant arterial disease is present can result in severe ischaemia in the leg,

with risk of necrosis. Consequently ABIs are routinely obtained for all patients with incident ulcers under the care of each of the trial centres taking part in the proposed trial, to confirm suitability for compression therapy. An ABI will be obtained from the clinical records for each participant. Where a potential participant already in treatment has an ABI obtained more than three months prior to the eligibility screen, a new ABI will be obtained prior to inclusion to ensure no development or progression of arterial disease.

- Clinical history and concomitant medications.
- Compression system: Details of the patient’s current treatment regime will be recorded.
- Health-related quality of life (HRQoL) instruments: The RAND 36-item Health Survey⁵¹, EQ5D,⁵⁴ and the Charing Cross Venous Ulcer Questionnaire (CXVUQ)⁵² will be administered.

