11.2 Statistical Analysis

All statistical analyses will be performed using SAS version 9.3 (SAS Institute Inc. Cary NC) Data analyses will be specified *a priori* in a statistical analysis plan (SAP) prepared by the trial statistician (and agreed upon by all members of the Steering Committee). The SAP will be available as a public domain document. Data from the Case Record Forms (CRFs) will be entered into password secured Oracle databases hosted by NIHI via the web by the Research Nurse. The data will be extracted into SAS for analysis on the trial's completion. No interim analyses are planned.

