11.2.1 Baseline Characteristics

Data on demographic characteristics (sex, age, self-reported ethnicity), history of ulceration, ulcer size, clinical history, current treatments (including compression system) and health-related quality of life will be collected. Since any differences between randomised groups at baseline could only have occurred by chance, no formal significance testing will be conducted.

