11.2.2 Treatment effect

All data analyses will be carried out on an intention-to-treat basis⁶³. Time-to-event data will be analysed using Kaplan Meier plots and log rank test, and Cox regression will be used to take into account known covariates and the varying times since randomisation. The assumption of proportionality will be checked using standard graphical techniques. Simple incidence rates, relative risks, absolute risks and numbers needed to treat, and 95% CIs will be obtained for all binary outcomes in the first instance, with subsequent multiple logistic regression analysis conducted if necessary to adjust for imbalance in covariates. Continuous outcomes will be analysed using multiple linear regression and adjusted for baseline value and other covariates if needed. Adverse events will be analysed using incidence rate ratios. A *kappa* will be calculated for the evaluation of the efficacy of blinding. Should aspirin prove effective in the primary analysis, heterogeneity of effects on time to healing will be analysed using subgroups specified *a priori* in the Statistical Analysis Plan.

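### Binary outcomes are adjusted only when covariates look imbalanced, a rule that will almost never pick up the stratified prognostic index; adjusting for centre and index in advance is a small gain at no cost in patients

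*Protocol*

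**What the plan says.** Protocol section 11.2.2 gives simple incidence, relative risk, absolute risk and number needed to treat for binary outcomes first, "with subsequent multiple logistic regression analysis conducted if necessary to adjust for imbalance in covariates". The statistical analysis paragraph of the synopsis repeats the rule: "with multiple logistic regression analysis if necessary to adjust for imbalance". Neither place names covariates or a threshold. Section 11.2.1 excludes a test as the trigger: "Since any differences between randomised groups at baseline could only have occurred by chance, no formal significance testing will be conducted".

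Section 7 specifies "stratified blocked randomisation with varying block sizes of 2 and 4", by trial centre and prognostic index, in order to "ensure a balance on key prognostic variables known to influence healing at 24 weeks". Section 10.1 defines the index (scores 0, 1 or 2 from ulcer area and duration) and says these two factors "provide data for a prognostic index for VLU healing with 24 weeks of compression". The Cox regression in section 11.2.2 takes known covariates into account with no imbalance condition.

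**The concern.** The protocol balances by design the variable that it regards as important for 24-week healing, and then adjusts binary outcomes only for what turns out imbalanced. The two choices work against each other. Covariate adjustment gains precision because a covariate predicts outcome, whether or not it is imbalanced. When randomisation is stratified on a prognostic factor, an analysis that ignores the factor overstates the variance of the treatment effect.

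Two things are at stake, both modest. The unadjusted interval for the proportion healed is a little too wide and its test a little conservative. And any adjusted result would depend on which covariates happen to look different in the baseline table. Raw ulcer area and duration can still differ within the coarse index levels, so ulcer severity is not wholly beyond the trigger, but the index itself practically is.

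**Working it through.** **The plan's own figure.** The protocol states no power for the proportion healed. Its sample size is set on time to healing. Medians of 92 and 64 days give a hazard ratio of 92/64 = 1.4375. The Schoenfeld formula at two-sided 0.05 and 90% power gives 320, against the stated 318, and 318/0.9 = 353.3, which rounds up to 354 (177 per arm). The medians and the total are used below.

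**Step 1: can the rule select the index?** With blocks of 2 or 4, the arms differ by at most 2 within a stratum. Five centres by three index levels make 15 strata, so the arms differ by at most 5 × 2 = 10 people at any index level. Allocation was simulated with N = 354, centre shares from the projected patient numbers in section 11.1 (324, 447, 222, 180, 252), and three assumed index splits, 5,000 runs each. The thresholds of 3 and 5 percentage points are also assumptions.

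| Arm difference | 5 points or more | 3 points or more |
|---|---|---|
| Any index level, stratified as planned | 0 of 5,000 for each split | 0.18%, 0.26%, 0.42% |
| Any index level, if not stratified | 54–60% | 77–81% |
| Independent covariate, 50% prevalence | 36–37% | 56% |

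A marker of large ulcers that varies within index levels (assumed prevalence 0/35/60% at index 0/1/2) differed by 5 points or more in 13–25% of runs.

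**Step 2: healing rates.** Under exponential healing over 168 days:
- control: 1 − 0.5^(168/92) = 0.718
- aspirin: 1 − 0.5^(168/64) = 0.838
- with 10% lost and counted as unhealed (section 11.2.4): 0.9 × 0.718 = 0.646 and 0.9 × 0.838 = 0.754

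The log relative risk is ln(0.754/0.646) = 0.1545 (RR 1.167).

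**Step 3: index effect (assumed).** The protocol gives no healing rates by index. Take an index split of 40/35/25% and let each index point multiply the odds of healing among followed participants by 0.61 or 0.37. Healing among those followed at index 0/1/2 is then:
- 0.61: control 0.800/0.709/0.598, aspirin 0.892/0.835/0.755
- 0.37: control 0.871/0.714/0.480, aspirin 0.937/0.845/0.669

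Each rate is multiplied by 0.9 for loss.

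**Step 4: variance, type I error and power.** With n = 177 per arm and no centre effect:
- unadjusted variance V_u = sum over arms of (1−p)/(np) = 0.004936 (SE 0.0703)
- true variance V_t replaces p(1−p) by its mean within index levels: 0.004843 (SE 0.0696) for 0.61, 0.004589 (SE 0.0677) for 0.37
- SE ratio √(V_u/V_t): 1.009 and 1.037
- under the null, with control rates in both arms, the SE ratio is 1.011 and 1.044, so type I error P(|Z| > 1.96 × ratio) is 0.0475 and 0.0406
- unadjusted power P(Z > (1.96√V_u − 0.1545)/√V_t): 0.595 and 0.598
- adjusted power P(Z > 1.96 − 0.1545/√V_t): 0.602 and 0.626

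The loss is 0.7 and 2.8 points.

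**Step 5: sensitivity.**
- Index splits 25/40/35 and 60/25/15: type I error 0.048 (0.61) and 0.040–0.042 (0.37); power loss 0.6–0.7 and 2.3–3.0 points.
- No loss to follow-up: type I error 0.047 and 0.037; power 0.769 v 0.777 and 0.778 v 0.810.
- Multipliers applied after counting losses as unhealed, an upper bound: type I error 4.6% to 3.6%, loss 1 to 5 points. At 0.37 this needs 99% of followed aspirin participants at index 0 to heal.
- Simulated trials with stratified blocks and a standardised logistic model on centre and index (4,000 per cell): type I error 0.048 and 0.040 unadjusted, 0.053 and 0.052 adjusted; power 0.599 and 0.600 unadjusted, 0.611 and 0.629 adjusted.
- A separate simulation without loss, with a conditional odds ratio of 2 and assumed control healing of 80/72/60, 90/70/40 or 85/65/35% by index: power rose from 75.5% to 77.6%, 63.0% to 70.2% and 69.7% to 75.5%. An extreme pattern of 95/70/20% gave 40% to 63%.

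**The case against.** The strongest reply is that this belongs to the SAP. Section 11.2 says the analyses will be specified in advance "in a statistical analysis plan (SAP) prepared by the trial statistician", and covariates for a supplementary model of a secondary outcome are normal SAP content. The absence of a threshold and a covariate list is therefore no defect, and none is claimed. What stands is that the protocol does state a selection rule, namely imbalance, and it is a poor one for this design. If the SAP fixes the covariates, the two documents differ and should be aligned; if it follows the protocol, the weakness carries over.

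It can also be said that the lead estimate is already fixed, unbiased and if anything conservative, and that the imbalance clause is meant for covariates outside the strata. Both are true, and they keep the point minor. But balance by design does not deliver the precision; that comes only from carrying the factor into the analysis.

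The size is indeed built on assumptions. At a multiplier of 0.8 the gain is 0.1 point of power. The interval around RR 1.167 is 1.017–1.339 unadjusted, against 1.018–1.338 (0.61) or 1.022–1.333 (0.37) with the index taken into account. The 36% figure likewise depends on a 5-point threshold that the protocol does not set.

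Finally, plain logistic regression would replace the relative risk by a conditional odds ratio, and dropping centre when events are sparse is itself a choice that needs a rule. Both are dealt with in the wording of the change.

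**Conclusion.** The point holds and is minor. Under stratified blocks of 2 and 4, a rule triggered by imbalance will practically never select the prognostic index. For the proportion healed at 24 weeks, omitting the index makes the standard error about 1% to 4% too large, takes type I error to 4.7% or 4.1%, and costs about 1 to 3 points of power. This rests on the assumed odds multipliers of 0.61 and 0.37, the assumed index splits, exponential healing and 10% loss counted as unhealed. Stronger assumed index effects give more, and nothing is lost if the index is not prognostic. The unadjusted estimate remains unbiased, the sample size is not set on this outcome, and the primary Cox analysis is not affected.

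**What to change.** In section 11.2.2 and the synopsis, replace the imbalance trigger with adjustment for centre and prognostic index fixed in advance. Report the adjusted relative risk and risk difference with 95% CIs, for example by standardising the logistic model, beside the unadjusted relative risk, absolute risk and number needed to treat. State in advance which estimate leads, and the event count below which the model uses the index alone. If the SAP already fixes these covariates, bring the protocol wording into line with it.

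The cost is one sentence in each place. Both factors are recorded at randomisation, so no extra data or participants are needed.

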9.1 Primary outcome measure

Time to complete healing (defined as intact skin without a scab) is recommended as an outcome to be included in research by the Cochrane Collaboration Wound Review Group and a 24 week follow up period is considered a minimum. Time to event data will be obtained from clinical records. District nurses visit patients on a weekly basis as part of normal care and record healing (average number of district nurse visits was 1.1 per week in the HALT trial). At 24 weeks, the Research Nurse will determine if the reference ulcer is healed. If the reference ulcer is healed, the research nurses will access clinical records to determine the date of healing was first reported during the 24-week period. If the reference ulcer is unhealed, the Research Nurse will determine from the clinical record whether the reference ulcer had healed at any time prior to 24 weeks. If there is no mention of healing then the ulcer will be assumed to have been unhealed during the 24 weeks. If the reference ulcer is recorded as healed during that time, the unhealed ulcer will be assumed to be a recurrent ulcer and the date healing is first recorded will be assumed to be the healing date.

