9.2 Secondary outcome measures

The following secondary outcome measures will be assessed in all participants at 24 weeks after randomisation:

- Proportion of participants with a healed reference VLU at 24 weeks.

- Estimated change in ulcer area – obtained from measuring maximum width and length of reference ulcer at baseline and endpoint and the ulcer area at each time point estimated using the calculation for area of an ellipse.⁵⁰ See rationale above for not using more complex methods of ulcer measurement.
- Change in HRQoL: Measured at baseline and at 24 weeks. Each person's perception of his or her general health will be assessed using the RAND 36-item Health Survey (a version of SF-36), EQ5D and ulcer-related health using the CXVUQ.^{51,52} The EQ5D and SF-36 are well-validated questionnaires for assessing quality of life in New Zealand and generating utility values for economic analyses.^{53,54 55,56} However, they may not be as responsive as a disease-specific instrument to changes in ulcer state (healed *versus* unhealed) over the short-term.^{22,57} Consequently, the CXVUQ will also be used, as it has been found to be very responsive to changes in VLU healing state.²²
- Adverse events: Measured throughout the 24-week follow up. Standard definitions of adverse events will be used and adverse events reports will be reviewed by one of the medically-qualified co-investigators and coded using the ICD-10 AM. All participants will be issued with a Clinical Trial Card, stating their participation in the trial and the possibility they are receiving low dose aspirin. If the participant presents with signs and symptoms of a serious adverse event, such as myocardial infarction, stroke, or extra-cranial bleed, the Clinical Trial Card will recommend they discontinue trial treatment and appropriate treatment initiated. These participants will still be included in follow up at 24 weeks.
- Treatment adherence: Measured at 24 weeks by count of remaining capsules by the Research Nurse.
- Efficacy of blinding: Measured at 24 weeks, the efficacy of blinding will be tested by asking patients which treatment they believed they received, and asking the same question of the research nurses.

10. Data collection and follow-up

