11.1 Sample Size

We estimate that 354 participants will be required. A sample size of 318 would be sufficient to show a **four week** difference in time-to-healing at 90% power with an alpha of 0.05, assuming the median time-to-healing in the control group over a six month follow up is 92 days (the median time to healing suggested by a previous bandaging trial for VLU patients over 24 weeks).⁶⁰ These data equate to a hazard ratio for VLU healing of 1.45, which is smaller than that suggested by our re-analysis of data from a cohort in a previous VLU trial (hazard ratio for VLU healing 1.77 for 150 mg dose). A four week difference was the minimal important difference that would most frequently

persuade people to use aspirin in a small commissioned survey of older people in Auckland, was the time interval used in a Canadian venous ulcer trial (<http://clinicaltrials.gov/ct2/show/study/NCT00202267>) and is lower than clinically significant differences used to calculate the sample sizes in two large venous ulcer trials conducted in the United Kingdom (the VenUS II and III trials^{61,62}). Although both the HALT trial and the PREPARE Pilot achieved very high follow up rates (99% and 100%),^{8,34} we have allowed for 10% loss to follow up, and thus a sample of 354 (177 in each group) will be required. Even if recruitment were lower than anticipated, using the same assumptions as above, a sample of 238 inflated to 264 (132 in each group) to allow for 10% loss to follow up would be sufficient to show a four week difference in time to healing with 80% power with an alpha of 0.05.

We assume that 70% of patients presenting with leg ulcers to the trial centres will have VLU. This assumption is supported in the literature^{5,6} and in an audit of patients presenting to the Nurse Maude Association in Christchurch in 2010 (pers. comm., [name], see below).

- In Auckland DHB, the most recent data (2011) shows the service received 309 referrals from multiple sources (mainly general practitioner and internal sources). Extrapolating this data to the 18 month recruitment period, Auckland DHB would receive 463 new assessment requests of which 324 new patients would have VLU, assuming 70% of these referrals had venous ulceration.

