14.5 Treatment on completion of trial

Participants will be asked to return all unused aspirin capsules to the research nurse. Returned capsules will be disposed of at the end of the trial follow-up period by the Research Nurse in accord with local DHB protocol.

15. Relevance to Health

The trial contributes to the goal of improving outcomes for individuals and populations with disease as follows:

- *More people could be healed* - Even with good compression 30-60% of patients remain unhealed after 12 weeks of compression therapy in clinical trials.²⁴⁻²⁷ New Zealand trials suggest a baseline healing rate of 50% at 12 weeks and aspirin could increase this proportion to 65% at 12 weeks and 75% at 24 weeks.
- *Improved quality of life* - Ulcer healing improves quality of life,²² and earlier healing will increase patients' quality of life, especially in the older people who more commonly have leg ulcers.

The trial also contributes to the goal of cost-effective sustainable solutions as follows:

- *Reduced costs* - The average cost of 12 weeks venous ulcer treatment is NZ\$972, a figure inflated by patients that remain unhealed. The average cost of healed patients for a 12-week period is NZ\$535 compared to NZ\$1405 for those that remain unhealed.⁸ Increasing the number of patients healed early will decrease the overall spend on this patient group.
- *Reduced burden on district nursing services* - As people's ulcers heal they no longer need district nursing and other related services for leg ulcer management, freeing up these resources.
- *Easier access to a low cost, effective adjuvant* - Aspirin is a safe, inexpensive, over-the-counter medication, with very few barriers to patient use or practitioner recommendation.

16. Dissemination of Results

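### Is baseline-adjusted linear regression the wrong method for change in ulcer area, when most ulcers will have closed to zero area by week 24?

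*Protocol*

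**What the plan says.** The synopsis lists "Change in estimated reference ulcer area from baseline to 24 weeks" as a secondary outcome. Section 9.2 includes all participants, healed or not, with area "obtained from measuring maximum width and length of reference ulcer at baseline and endpoint" and computed as an ellipse. Section 11.2.2 gives one sentence for every continuous outcome: "Continuous outcomes will be analysed using multiple linear regression and adjusted for baseline value and other covariates if needed". It names no scale, neither raw cm² nor a log or percentage scale, and no rank method. Section 11.2 leaves the detailed specification to a statistical analysis plan, which is not among the documents available here.

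The synopsis also states: "Complete healing is defined as full epithelialisation of the ulcer with no scab". A healed ulcer therefore has area zero.

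**The concern.** Read at face value, the outcome is absolute change in cm². Most participants would then have a change equal to minus their baseline area, and the rest would be scattered according to how large their unhealed ulcer still is. With baseline area in the model, regressing change gives the same treatment coefficient as regressing week-24 area, because change is week-24 area minus a covariate already in the model. The regression therefore compares means of a variable with a large spike at zero and perhaps a long right tail.

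Two things would be at stake. A real effect on area could be missed because a few large unhealed ulcers inflate the residual variance, or the estimate could turn on those few ulcers. Only a secondary outcome is involved; the time-to-healing analysis is untouched.

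**Working it through.** **Inputs.** Section 11.1 gives the control median, "assuming the median time-to-healing in the control group over a six month follow up is 92 days", and a four-week difference, so 92 − 28 = 64 days on aspirin. The ratio 92/64 = 1.44 agrees with the stated hazard ratio of 1.45. Follow-up is 168 days. Section 15 says "aspirin could increase this proportion to 65% at 12 weeks and 75% at 24 weeks", from a base of 50% at 12 weeks. The protocol gives no standard deviation, distribution or power for ulcer area, so there is no figure of its own to reproduce for this outcome.

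**Share of zeros**, assuming constant hazards:

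- Control: 1 − 2^(−168/92) = 71.8%.
- Aspirin: 1 − 2^(−168/64) = 83.8%.
- Mean: (71.8 + 83.8)/2 = 77.8%.
- From Section 15 instead: the 12-week hazard ratio is ln(0.35)/ln(0.50) = 1.51. With aspirin at 75%, control is 1 − 0.25^(1/1.51) = 60%, and the mean is 67.5%.

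Recurrence, which Section 9.1 recognises ("the unhealed ulcer will be assumed to be a recurrent ulcer"), would lower these shares somewhat. Zeros remain a clear majority, so the premise is right.

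**Validity.** The treatment coefficient is a baseline-adjusted difference in mean area. Randomisation makes that comparison fair whatever the shape of the distribution. At 159 per arm (318/2), simulated type I error was 3–6% for every method tried.

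**Power.** These simulations rest on assumptions that are not in the protocol: lognormal baseline area with median 4 cm²; unhealed ulcers at a median of 60% of baseline (log-SD 0.6); 40% of ulcers older than six months; placebo healing set at 71.8%; healing either unrelated to area or slower in larger ulcers. The van Elteren test compares percentage change, stratified by prognostic index (Section 10.1: "The index assigns scores of 0, 1 or 2 based on absence of both factors").

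| Analysis (log-SD of baseline area 1.0–1.6) | Aspirin affects healing only | Aspirin also shrinks unhealed ulcers by 30% |
|---|---|---|
| Linear regression, cm² | 10–31% | 32–62% |
| Linear regression, log(1 + area) | 40–61% | 65–81% |
| Linear regression, percentage change | 47–56% | 90–92% |
| van Elteren test | 60–73% | 75–83% |
| Healed proportion (already listed) | 61–74% | 61–74% |

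With light-tailed areas (log-SD 0.5), the cm² regression has 44–49% against 70–74% for van Elteren when only healing is affected. With shrinkage as well, it has 82–85% against 79–82%. Repeat runs differ by a few points (87–90% against 83–85% in one) but keep that order.

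**Reading the table.**

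1. The low figures belong to the cm² scale, not to linear regression. Two other linear regressions, both compatible with the wording of Section 11.2.2, recover much or all of the loss.
2. No method is best throughout. The rank test leads the regressions when aspirin affects healing only, but there it merely matches the healed-proportion outcome, because most of its ranks are tied at −100%.
3. Area adds information beyond healing when aspirin also acts on unhealed ulcers. There, linear regression of percentage change beats the rank test at every log-SD from 0.5 to 1.6 (91–96% against 74–85% in a run over that whole range).

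**Influence of large ulcers.** At log-SD 1.0–1.6 the largest 5% of squared residuals carry 77–92% of the residual sum of squares, so the cm² analysis does lean on few ulcers. In a separate simulation (median 3 cm², log-SD 0.3–1.5), removing the three largest week-24 areas moved the estimate by about 0.4 of its standard error. That is noticeable, but not enough to make the result arbitrary.

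**The case for a change.** The strongest case for the concern is that absolute change in cm² is the natural reading of the outcome, and that Section 11.2.2 offers no flexibility beyond extra covariates. A long tail is plausible: eligibility sets no limit on ulcer size, the largest ulcer is the reference, and Section 10.1 treats large area as a marker of slow healing, so large ulcers should be over-represented among the unhealed. When aspirin affects healing only, the cm² analysis has the lowest power under every area distribution tried. With the other set of assumptions (median 3 cm², log-SD 0.3–1.5) it has 9–39%, against 57–72% for a rank-based covariance analysis. Changing the test would need no new data.

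The premise and the direction of these results stand. They do not establish a fault in the protocol. The sentence does not commit the trial to cm², and settling the scale is ordinary work for the analysis plan. The suggested replacement also has a price. It gives up a mean difference in area as the main result, largely repeats an outcome already listed, and loses a few points of power when areas are light-tailed and aspirin shrinks unhealed ulcers.

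**Conclusion.** The concern does not hold. The protocol's figures do imply that about 67–78% of week-24 areas would be zero, before loss and recurrence and under constant hazards. But the planned regression is valid, type I error stays near 5%, and the primary conclusion is not affected. The size of any inefficiency cannot be read from the protocol: power on the cm² scale ranges from 10% to 90% over assumed area distributions and assumed effects on unhealed ulcers. Choosing among raw, log, percentage and rank analyses for a secondary outcome on which the trial was not powered is a question of what one wants to estimate, and reasonable statisticians differ on it. The protocol states nothing wrongly here, contradicts nothing, and leaves the scale open for the analysis plan.
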